- a. By history, patient reports that they received no subjective benefit from two different categories of anti-Parkinsonian medications, including: levodopa replacement, dopamine agonists, anticholinergic agents, amantadine. If subject is on therapy at present, the current therapy could count towards quantifying the medications which have failed to reduce tremor, so long as tremor amplitude meets inclusion criterion “4”. Patient will be asked whether, on average, they believe their tremor has been consistently disabling over the course of the last month.
- b. Medication refractoriness will be confirmed through observation at time of peak-dose effect of one of the reported oral agents which have failed to reduce tremor. Note that within-individual intermittency and variability of rest tremor can be influenced by anxiety, stress, cold temperature, and fatigue. In an effort to reduce this variability, we will examine subjects in a comfortable area of the clinic space, providing up to 20 minutes to allow them to relax in a temperature-neutral location, and reduce anxiety.
- c. If at peak-dose effect the subject is felt to still meet inclusion criterion “4”, they will remain a possible candidate for the study.
- d. Once the movement disorder specialist considers the subject a possible candidate, the rest tremor amplitude will be assessed using the Px1. This assessment should be completed within 10-20 minutes of the assessment by the rating movement disorder specialist

7. Participants must be able to make no changes to their anti-parkinsonian medications for 150 days (study duration). Ability and safety to do so must also be determined by the participant’s treating physician and confirmed in writing prior to participating.
8. Able to provide informed consent

Exclusion criteria:

1. History of having undergone botulinum toxin injections for any other condition previously
2. Allergy to carbidopa or levodopa.
3. Prescreening Montreal Cognitive Assessment (MoCA) score less than 22
4. Prescreening muscle weakness as determined by Medical Research Council grade less than 5/5 on direct testing in the upper limb afflicted with rest tremor.

5. Pregnancy: documentation of non-pregnancy by urine pregnancy test will be obtained from all women of child-bearing potential prior to participation
6. Infection at the proposed injection site
7. Those with a pre-existing, concomitant neuromuscular disorder
8. Compromised respiratory function

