- a. Participant will be asked to come to clinic at the time they are due for their next dose of anti-Parkinsonian medication. If they are not taking anti-Parkinsonian medication, a single dose of carbidopa/levodopa 25/100mg 1 tablet will be administered. They will only take medication when instructed. Then at peak-dose effect of the medication taken:
- b. Repeat MDS-UPDRS tremor subscore obtained by movement disorder specialist
- c. Repeat muscle strength assessment of limb: using MRC muscle testing via physical examination
- d. Repeat ARAT score obtained by occupational therapist
- e. The Px1 will be used to obtain information regarding the direction of oscillation, average amplitude, peak amplitude, and frequency of the tremor.

- f. Based on enrollment randomization from Visit 1, and after all above measures have been obtained:
 - i. If sham injection was performed at Visit 1, then onabotulinum toxin injection is performed at Visit 3 and vice versa. The same injection paradigm used in Visit 1 will be used for Visit 3 to ensure greatest level of consistency between injections.
 - g. Patient will complete a daily diary of symptoms for 30 days starting the day AFTER the study visit, to be collected by study personnel at the following study visit. The diary includes subjective assessments of tremor severity, tremor persistence, arm weakness, and arm dysfunction.
- h. **Visit 4: Day 120 (+/- 6 days per visit)**
 - a. Participant will be asked to come to clinic at the time they are due for their next dose of anti-Parkinsonian medication. If they are not taking anti-Parkinsonian medication, a single dose of carbidopa/levodopa 25/100mg 1 tablet will be administered. They will only take medication when instructed. Then at peak-dose effect of the medication taken:
 - b. Repeat MDS-UPDRS tremor subscore obtained by movement disorder specialist
 - c. Repeat muscle strength assessment of limb: using MRC muscle testing via physical examination
 - d. Repeat ARAT score obtained by occupational therapist
 - e. The Px1 will be used to obtain information regarding the direction of oscillation, average amplitude, peak amplitude, and frequency of the tremor to then be compared to Visit 3.
 - f. Patient will complete a daily diary of symptoms for 30 days starting the day AFTER the study visit, to be collected by study personnel at the following study visit. The diary includes subjective assessments of tremor severity, tremor persistence, arm weakness, and arm dysfunction.

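### The urine pregnancy test and the site-infection and respiratory exclusions are not repeated before the Visit 3 injection, so in sequence BA they precede saline and the only toxin dose follows at least 84 to 96 days later

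*Combined protocol and SAP*

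**What the plan says.** Under III. Subjects, Exclusion criteria, item 5 requires that "documentation of non-pregnancy by urine pregnancy test will be obtained from all women of child-bearing potential prior to participation". Items 6 and 8 exclude "Infection at the proposed injection site" and "Compromised respiratory function". Screening against these criteria is a listed step only at Visit 1 (IV. Research Plan, iii. Study Design, e. Visit 1, item a). The Recruitment & Consent section allows screening to fall on an earlier day than the first study visit.

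At Visit 3 (same section, g. Visit 3, items a to g) the order is medication timing, tremor subscore, MRC strength, ARAT, Px1, injection, diary. The only condition attached to the injection is in item f: "Based on enrollment randomization from Visit 1, and after all above measures have been obtained". Item f.i then assigns the treatment: "If sham injection was performed at Visit 1, then onabotulinum toxin injection is performed at Visit 3 and vice versa". Sequence BA is placebo at Visit 1 and Botox at Visit 3.

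VII. Safety Monitoring Plan adds adverse-event monitoring by the principal investigator, weekly calls for four weeks after each injection visit, and a halt of the whole study after a serious adverse event that raises risk. It contains no rule for withholding the second injection from an individual.

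**The concern.** A test or exclusion checked at entry describes the participant at entry. In sequence AB that is close to the toxin dose. In sequence BA it is close to a saline dose, and toxin is given about three months later with no listed repeat. A participant who became pregnant in between, or whose breathing had deteriorated, could reach the toxin injection without a protocol step that looks for it. The injector does not know what is in the syringe and has no written rule for holding it back, so the decision would rest on individual judgement and could differ between participants. The stake is participant safety at one injection. The treatment comparison is not at issue.

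**Working it through.** The plan gives no figure for this point, so the check is visit-window arithmetic plus a comparison of the relevant sections.

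**Inputs.** Visit 1 is Day 0. Visit 2 is Day 30 ± 6 and Visit 3 is Day 90 ± 6 (visit schedule). Calls run weekly for four weeks after an injection visit (Safety Monitoring Plan). There are 16 participants aged 45 to 80 (III. Subjects). The allocation ratio is not stated.

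**Age of the entry checks at the toxin dose in BA.** Earliest: 90 − 6 = 84 days. Latest: 90 + 6 = 96 days. Both count from Day 0. Any interval between screening and Visit 1 is added, so these are minimum gaps for the two ends of the window.

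**Last scheduled contacts before toxin in BA.**
- Calls: 4 × 7 = 28, so the last is at about Day 28. That is 84 − 28 = 56 to 96 − 28 = 68 days before toxin.
- Visit 2: Day 24 to 36. That is 84 − 36 = 48 to 96 − 24 = 72 days before toxin. Its steps include no pregnancy, infection or respiratory check.

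**The schedule table.** Its last row has six cells for five visits: Intervention, Safety Assessment, Intervention, then Safety Assessment three times. Injections occur only at Visits 1 and 3, so the reading that fits is:

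| Visit | Row content |
|---|---|
| 1 | Intervention |
| 2 | Safety Assessment |
| 3 | Intervention and Safety Assessment |
| 4 | Safety Assessment |
| 5 | Safety Assessment |

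So a Safety Assessment probably is planned at Visit 3. Nothing defines what it contains or says that it comes before the injection. The only safety review described in the visit steps is at Visit 5, and it concerns toxin wear-off.

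**Item by item at Visit 3.**
- Pregnancy: no listed step would detect it.
- Site infection: not listed, but a specialist examines and then needles the limb under EMG guidance and would probably see it. V. Benefits and Risks describes the procedural risks of saline as similar to those of toxin, so this item concerns second injections in both sequences.
- Respiratory compromise: depends on self-report, on what staff notice, or on the undefined Safety Assessment.
- Strength: MRC is repeated, but no grade leads to an action.

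**Cost of one withheld injection.** 1/16 = 6.25% of participants would lack a full toxin-versus-sham pair as treated.

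**The case against.** The strongest reply is that almost nothing follows in practice. With 16 participants aged 45 to 80, the test may apply to very few women or to none. Doses are capped at 50 units per limb. The documents give no rate for any of these contraindications. At Visit 3 a specialist rates the tremor and tests strength, an occupational therapist runs the ARAT, and Px1 measurements are taken before the needle goes in. Overt infection or marked breathlessness would be hard to miss. The Medical follow-up section sets out routes for medical problems, and calling the Visit 5 review the last one implies earlier ones. Leaving a contraindication to the injecting physician is ordinary practice in a single-centre pilot.

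Most of this stands, and it limits the point to a minor one. It does not supply a pregnancy test, and it does not define the Safety Assessment.

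A reader might infer more than the documents support:
- *That the protocol orders toxin despite a contraindication.* Item f.i fixes the crossover allocation and says nothing about overriding clinical judgement.
- *That no safety check exists between entry and toxin.* The calls, Visit 2, the repeated MRC test, adverse-event monitoring and the probable Visit 3 Safety Assessment say otherwise.
- *That a neuromuscular disorder arising during the study is also missed.* Exclusion 7 covers "Those with a pre-existing, concomitant neuromuscular disorder", so a new diagnosis would not breach it.
- *That participants receive no pregnancy advice.* The consent pages are not in the file and may contain it. This point concerns the Visit 3 steps only.

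**Conclusion.** The point holds as a minor, low-frequency safety improvement. The pregnancy test is required only before participation, and the Visit 3 steps repeat neither it nor the site and respiratory exclusions. In BA the only toxin dose therefore follows the test by at least 84 to 96 days. The main undetected item is a pregnancy that began after screening, which is likely very rare in this age range. The site-infection item is a needle risk in both sequences and would probably be noticed.

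This rests on two readings: that the Visit 3 list is complete as printed, and that the Safety Assessment has no defined content elsewhere. Under 1:1 allocation, which is an assumption, 16/2 = 8 participants would be in BA. That counts who is exposed to the timing, not who has a contraindication. No statistical figure in the plan changes.

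**What to change.** Add one step to Visit 3 before item f, identical in both sequences and carried out blind:

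- Repeat the urine pregnancy test in women of child-bearing potential.
- Confirm that there is no injection-site infection and no compromised respiratory function.
- If any of these is present, do not inject, and follow the participant to Visit 5 under the plan's intention-to-treat principle. A local infection may be re-checked within the existing Day 84 to 96 window.

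Do not make the second injection conditional on MRC 5/5. Weakness caused by period 1 toxin can arise only in AB, so that condition would hint at sequence and make missing second periods depend on treatment.

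The cost is a few lines of protocol text, a short checklist and a urine test for few or no women. The downside is an occasional missed second period, 1 of 16 pairs each time, including in AB, where the withheld injection would have been saline.

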 - a. Severity/Amplitude: As measured by the MDS-UPDRS tremor subscore.
 - b. Limb function: As measured by the Action Research Arm Test (ARAT)
2. Evaluate Px1 versus expert clinical assessment and its sensitivity to detect changes based on the MDS-UPDRS tremor subscore
3. Determine whether methodology for this pilot project can feasibly be applied to a larger subsequent study that could be adequately powered to detect a clinically-meaningful effect of onabotulinumtoxin A on medically-refractory rest tremor.

ii. **Hypotheses:**

1. (A) Onabotulinumtoxin A significantly attenuates the amplitude of medically-refractory rest tremor of the upper limb in Parkinson's patients as compared to sham injections; as measured by reduction in the MDS-UPDRS tremor subscore.
1. (B) Onabotulinumtoxin A significantly improves the limb function of Parkinson's patients with medically-refractory rest tremor of the upper limb as compared to sham injections; as measured by an increase in ARAT scores.

III. Subjects

i. **Pilot group**

- **Number – 16**
 - Due to the limitations brought on by internal funding for this pilot project and the overall cost of botulinum toxin, an even number of patients was chosen after a cost analysis was completed. It was determined that we could cover the cost of 16 participants throughout the proposed course of the study.
- **Gender** – male or female
- **Ethnicity** – all, no restrictions
- **Race** – all, no restrictions
- **Age** – 45-80

ii. **Eligibility Criteria**

Inclusion Criteria:

1. At least 45 years of age, and no more than 80 years of age.
2. Meet UK Parkinson's disease brain bank diagnostic criteria
3. Have clinical evidence of rest tremor of one or both upper extremities defined as involuntary, rhythmic oscillations about any joint within the upper extremities
4. Rest tremor amplitude must be at minimum 3 cm as determined by expert opinion by a movement disorders specialist. Confirmation of amplitude measurement will

be obtained from the Px1 prior to active participation in the study but will not be used for inclusion/exclusion in study participation.

5. Rest tremor must be historically refractory to at least 2 categories of medications typically used as anti-parkinsonian agents including levodopa formulations, dopamine agonists, amantadine, and anticholinergics.
6. **Determining Medication Refractoriness:**

AFTER patient is consented:

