Intervention	Safety Assessment	Intervention	Safety Assessment	Safety Assessment	Safety Assessment
--------------	-------------------	--------------	-------------------	-------------------	-------------------

iii. Study Design

- a. The study will comprise of a double blinded, crossover study where the subjects will serve as their own controls. There will be no medication changes made to Parkinson's disease medications throughout the subjects' participation in the study.
- b. **Randomization:** Determined by the IDS Pharmacy at UNC using a computer-generated algorithm which will determine whether subject's first intervention will be sham saline injections versus onabotulinum toxin A. The IDS Pharmacy will keep track of which agent was administered first to avoid administering same intervention twice.
- c. **Blinding:** Double-blinded study whereby the subject, the movement disorder specialist injecting neurotoxin, and the movement disorder specialist rating the patient will be unaware of the solution injected and/or planned for injection same day. To ensure that the injecting specialist is blinded to the solution, syringes will be premixed by the IDS Pharmacy and de-identified of any possible labels that would indicate the properties of the solution being administered to the subject.

Injection Sequence	Visit 1	Visit 3
Sequence AB	Botox	Placebo
Sequence BA	Placebo	Botox

- d. **Deciding between bilateral tremors:** The side to be studied shall be the limb with the tremor of greatest amplitude. This will be determined by a combination of factors: Participant self-report of which tremor is "worse", which tremor is "more disabling", as well direct observation by the examiner and the MDS-UPDRS tremor subscore per limb to determine which limb has the tremor of greatest amplitude. Once that limb is chosen, it shall be utilized throughout the duration of the study.

e. Visit 1: Day 0

- a. Screening, as per "Eligibility Criteria"
 - i. Participant will be asked to come to clinic at the time they are due for their next dose of anti-Parkinsonian medication. If they are not taking anti-Parkinsonian medication, a single dose of carbidopa/levodopa 25/100mg 1 tablet will be administered (this assumes participant meets exclusion criteria "b"). They will only take medication when instructed. Then at peak-dose effect of the medication taken:
- b. Baseline MDS-UPDRS tremor subscore obtained by movement disorder specialist

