No power calculation can be performed. This is a pilot feasibility study to determine if onabotulinumtoxin A can be utilized to reduce resting tremor amplitude and improve arm function.

Data Analysis (Performed by [name], PhD)

Note that all statistical analysis, and as such any missing data/values/dropouts, will be performed assuming an intention-to-treat principle. All statistical estimates will be tabulated along with corresponding confidence intervals (CIs). All hypothesis tests that are observed to be not statistically significant will be reported as being inconclusive. Lastly, all data acquired for Visit 5 will be utilized for review of safety. This is to ensure that the expected washout effect is occurring and that there is expected normalization of values trending towards or back to previous baseline values. For this reason, there is an absence of any testing with the Px1 on Visit 5 (since data will not be utilized to compare to previous visits for purposes of statistical analysis).

Specific Aim 1a. The change in tremor severity effected by onabotulinumtoxin A will be compared to the change effected by sham saline. Tremor severity will be measured via the MDS-UPDRS tremor subscore. A Student's t-test will be utilized to compare postintervention measures within subjects.

Specific Aim 1b. The change in limb function as measured by the ARAT created by onabotulinumtoxin A will be compared to the change created by sham saline. A Student's t-test analysis will be used to compare change in ARAT scores within subjects.

Specific Aim 2. The strength of the correlation between MDS-UPDRS tremor subscore and tremor characteristics as assessed by the Px1 will be obtained. Will then evaluate the strength of the correlation between the change in MDS-UPDRS score and change in the ARAT score. This latter correlation will then be compared to the correlation between the change in tremor characteristics as assessed by the Px1 and the change in the ARAT score.

Specific Aim 3. Pilot data will be reviewed and trends analyzed. Subsequent power analysis will be performed to determine size of study population that is necessary to adequately measure statistically significant effect. Data regarding dropout rates will also be reviewed to determine if study methodology needs to be adjusted for a larger study population.

Interpretation of Results

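### Dropouts are promised intention-to-treat handling, but the within-subject t-tests named for Aims 1a and 1b, with no missing-data method, in effect analyse complete pairs only

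*Combined protocol and SAP*

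**What the plan says.** The note that opens Data Analysis in section VI applies one principle throughout: statistical analysis, and with it "any missing data/values/dropouts, will be performed assuming an intention-to-treat principle". The tests follow in the same section. For Aim 1a: "A Student's t-test will be utilized to compare postintervention measures within subjects". For Aim 1b: "A Student's t-test analysis will be used to compare change in ARAT scores within subjects".

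Section IV.iii describes a "crossover study where the subjects will serve as their own controls", with the second treatment given at Visit 3 (Day 90): "If sham injection was performed at Visit 1, then onabotulinum toxin injection is performed at Visit 3 and vice versa". The post-injection assessments are Visit 2 (Day 30) and Visit 4 (Day 120). Visit 5 serves safety only.

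The sample size rests on budget (section III: "we could cover the cost of 16 participants throughout the proposed course of the study"), and section VI adds "No power calculation can be performed". Dropout comes up again only under Aim 3: "Data regarding dropout rates will also be reviewed to determine if study methodology needs to be adjusted for a larger study population". No imputation rule, mixed model, analysis-set definition or missing-data sensitivity analysis appears in the document.

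**The concern.** Intention-to-treat settles who is analysed and under which allocation. It does not supply a value for a period that was not observed. A within-subject t-test works on one difference per person, so a person with only one period has nothing to enter. Someone who leaves after Visit 2 is lost to the test although a valid first-period result exists.

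Two things are at stake: some precision in a study of 16, and possible bias if leaving is related to how the first period went. The toxin-sham contrast is meant to serve as preliminary data for grant proposals, and the pilot data feed the Aim 3 power analysis, so a distorted estimate would be carried forward.

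**Working it through.** **Which assessments each test needs**

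- Aim 1a, as the test is worded (post-injection values): Visits 2 and 4.
- Aim 1b, if change is taken from each period's own baseline: Visits 1, 2, 3 and 4. The same holds for Aim 1a if change is meant. Its opening sentence speaks of change, while its test sentence compares post-injection values.
- A missed Visit 5 has no effect on either test.

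**Inputs.** N = 16 is from section III. The document gives no dropout rate, alpha, SD or correlation, so there is no stated figure to reproduce. Assumed here: 8 participants per sequence, 2 or 4 leaving after period 1, within-subject correlation ρ of 0.3 to 0.7, and two-sided 5%.

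**1. Cost of losing pairs.** Take an effect of 0.75 SD of the within-subject differences, which 16 pairs detect with about 80% power. The 95% CI half-width is t(0.975, n-1)/√n. Power comes from the noncentral t with noncentrality 0.75√n.

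| Pairs | Half-width (SD of differences) | Power |
|---|---|---|
| 16 | 0.53 | 80.1% |
| 14 | 0.58 | 73.7% |
| 12 | 0.64 | 65.8% |

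**2. How much of that the analysis can recover.** Take a model with treatment and period effects, unit outcome variance and known variances. Let n₁, n₂ be the participants per sequence with period 1 data and m₁, m₂ those with both periods. Put N* = 1/(1/n₁ + 1/n₂), M = 1/(1/m₁ + 1/m₂) and r = (1+ρ)/(1-ρ).

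- Information from complete pairs only: (1+r)M.
- Information from all available data: N* + rM. The first term is the period 1 comparison in everyone; the second is period 2 given period 1 in those with both.
- Variance ratio, all data to complete pairs: (1+r)M / (N* + rM).

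With n₁ = n₂ = 8, N* = 4. Example with 4 dropouts, 2 per sequence, and ρ = 0.5: M = 3 and r = 3, so the ratio is 12/13 = 0.92.

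| Dropouts by sequence | M | ρ = 0.3 | ρ = 0.5 | ρ = 0.7 |
|---|---|---|---|---|
| 1 and 1 | 3.50 | 0.95 | 0.97 | 0.98 |
| 2 and 2 | 3.00 | 0.90 | 0.92 | 0.95 |
| 4 and 0 | 2.67 | 0.85 | 0.89 | 0.93 |

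The variance falls by about 2-5% with 2 dropouts (one per sequence) and 5-15% with 4. With dropouts split evenly and degrees of freedom of pairs minus 2, power for the same effect is 74-75% with 2 dropouts (against 73.7% for the paired test) and 67-70% with 4 (against 65.8%).

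**3. Bias in one assumed case.** Suppose the true effect is zero, there is no period effect, lower scores are better, and the worst 25% of period 1 results in the toxin-first sequence leave.

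- Mean period 1 result of those who stay in that sequence: -φ(0.674)/0.75 = -0.318/0.75 = -0.424 SD.
- Their mean toxin-minus-sham difference: -0.424(1-ρ).
- Their share of the complete pairs: 0.75/(0.75 + 1) = 0.429.
- Bias in the pooled mean difference: -0.424 × 0.429 × (1-ρ) = -0.182(1-ρ).

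This gives 0.13, 0.09 and 0.05 outcome SD in favour of toxin at ρ = 0.3, 0.5 and 0.7; a large simulation agrees. In this case leaving depends only on an observed result, so a likelihood analysis of all available data is unbiased: run with known variances, it gave a bias of 0.00 at all three correlations.

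**The case against.** The plan never says complete cases. A paired t-test could be run on all 16 if missing values were imputed, and an unstated imputation is not excluded. A reader might infer that the named test cannot deliver intention-to-treat handling at all; the text does not support that. But if imputation is meant, its method is undefined and the plan still needs amending. What stands is that the named test, run with nothing added, keeps only complete pairs.

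A reader might also charge the fall in power from 80% to 74% or 66% to the t-test. Most of it is the cost of losing people, and the choice of analysis recovers about 0 to 4 percentage points.

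It is tempting, too, to say that treatment-related dropout is likely, or that the plan expects dropouts. Neither is supported. Section V puts weakness at roughly 1-10% and calls it transient. With an assumed 8 participants receiving toxin first, that is 8 × 0.01 to 8 × 0.10, or 0.08 to 0.8 people, before asking whether any would leave. Aim 3 reviews dropout as a feasibility measure and states no anticipated rate. Outcome-related dropout is therefore a possibility to guard against, not a forecast.

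Finally, the mixed model is not the only repair. A defined imputation rule, or an open label of complete pairs, would also end the inconsistency.

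**Conclusion.** The concern holds in this form: the promised principle and the named tests do not match, and with no missing-data method stated, the analysis of Aims 1a and 1b is in effect one of complete pairs. This follows from the text and needs no assumed figure.

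Its size does rest on assumptions. The precision forgone is modest: 2-5% of variance with 2 dropouts and 5-15% with 4. The illustrated bias of 0.05-0.13 outcome SD belongs to one deliberately adverse dropout pattern. If every participant completes Visits 1 to 4, the effect is nil. The change is worth making because it is cheap and these estimates will inform the next study.

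**What to change.** Before unblinding, amend section VI as follows.

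- Replace both t-tests with a linear mixed model on all available Visit 2 and Visit 4 outcomes, analysed as randomised. Use fixed effects for treatment and period, a random participant effect, and small-sample degrees of freedom (for example Kenward-Roger).
- For each aim, state whether the outcome is the post-injection value or the change, and how each period's baseline enters the model.
- State that validity rests on data being missing at random. The model does not fully protect against dropout driven by unobserved outcomes.
- State that randomised participants with no post-injection value are reported but contribute no outcome.
- Report toxin minus sham with a 95% CI.
- Keep the paired t-test as a sensitivity analysis, labelled as complete pairs.

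The cost is SAP wording, slightly more analysis work and a model assumption. No visits, participants or data are added.

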- c. Baseline muscle strength assessment of limb: using Medical Research Council (MRC) muscle testing via physical examination
- d. Baseline ARAT score obtained by occupational therapist

- e. The Px1 will be used to obtain information regarding the direction of oscillation, average amplitude, peak amplitude, and frequency of the tremor. This will only serve as objective information regarding the tremor
- f. Randomization is performed for Visit 1, and after all above measures have been obtained the subject will be injected with either sham normal saline injection using 0.9% normal saline solution (no greater than 2 mL total solution) or predetermined onabotulinum toxin doses based off of affected muscle groups. Refer to table below for information regarding predetermined dosing.
- g. Patient will complete a daily diary of symptoms for 30 days starting the day AFTER the study visit, to be collected by study personnel at the following study visit. The diary includes subjective assessments of tremor severity, tremor persistence, arm weakness, and arm dysfunction.

f. Visit 2: Day 30 (+/- 6 days per visit)

- a. Participant will be assessed when they are due for their next dose of anti-Parkinsonian medication. If they are not taking anti-Parkinsonian medication, a single dose of carbidopa/levodopa 25/100mg 1 tablet will be administered. They will only take medication when instructed. Then one hour after observing a dose of anti-Parkinsonian medication (i.e. at peak-dose effect of the medication taken):
- b. Repeat MDS-UPDRS tremor subscore obtained by movement disorder specialist
- c. Repeat muscle strength assessment of limb: using MRC muscle testing via physical examination
- d. Repeat ARAT score obtained by occupational therapist
- e. The Px1 will be used to obtain information regarding the direction of oscillation, average amplitude, peak amplitude, and frequency of the tremor to then be compared to Visit 1.
- f. Patient will complete a daily diary of symptoms for 30 days starting the day AFTER the study visit, to be collected by study personnel at the following study visit. The diary includes subjective assessments of tremor severity, tremor persistence, arm weakness, and arm dysfunction.

g. Visit 3: Day 90 (+/- 6 days)

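### Aim 1b tests raw change in ARAT, which on the natural reading subtracts two single-visit baselines in a crossover; adjusting for the baseline difference is usually more precise and needs no new data

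*Combined protocol and SAP*

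**What the plan says.** Section IV.iii a describes the design: "The study will comprise of a double blinded, crossover study where the subjects will serve as their own controls". Injections are given at Visits 1 and 3 in AB or BA order.

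Section VI, Data Analysis, sets the Aim 1b comparison: "The change in limb function as measured by the ARAT created by onabotulinumtoxin A will be compared to the change created by sham saline". The test follows: "A Student's t-test analysis will be used to compare change in ARAT scores within subjects". No covariate, period term or sequence term is named.

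Aim 1a is mixed. It opens with change: "The change in tremor severity effected by onabotulinumtoxin A will be compared to the change effected by sham saline". Its test sentence then uses a different quantity: "A Student's t-test will be utilized to compare postintervention measures within subjects".

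The first-period baseline is one ARAT reading at Visit 1: "Baseline ARAT score obtained by occupational therapist". One further ARAT is taken at Visit 3 before the second injection, and the visit table in Section IV.ii labels that visit a baseline too. Only the Px1 text says which visits are paired (2 with 1, 4 with 3), and only Px1 readings are averaged in threes (Section IV.iii l).

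The sample size comes from the budget (Section III.i): "It was determined that we could cover the cost of 16 participants throughout the proposed course of the study".

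**The concern.** In an AB/BA crossover the comparison of the two post-injection scores already removes stable differences between participants. Subtracting a separate baseline in each period brings in two more single readings and fixes their weight at 1. If those readings say little about the later score beyond what the participant's own level already says, the subtraction adds noise and removes none. An estimated slope avoids having to guess.

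With the sample capped by cost, lost precision cannot be bought back. It would show as wider confidence intervals for Aim 1b. If the SD of the change contrast feeds the Aim 3 power analysis, it could also distort the planned size of the next study. Section VI, Interpretation of Results, lists dropping the toxin for this purpose among the possible readings of a failure to show a difference, so precision matters even in a pilot.

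A second issue is residual toxin effect at Visit 3. Section V expects the effect to last up to three months, and Visit 3 may fall as early as Day 84 (90 - 6). In sequence AB, any effect still present at Visit 3 that fades by Visit 4 would count as worsening under sham.

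**Working it through.** The plan states no power, effect size, SD or correlation, so there is no figure to reproduce.

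**Inputs from the documents:** 16 participants; AB/BA design; visits at Days 0, 30, 90 and 120.

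**Assumptions:** 8 per sequence, two-sided 0.05, equal variance s² at each visit, and the correlations shown below.

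Let B1, P1, B2, P2 be the scores at Visits 1, 2, 3 and 4, with correlation w within a period and b for every pair across periods.

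- Post-injection contrast P1 - P2: variance 2s²(1-b).
- Change contrast (P1-B1) - (P2-B2): variance 4s²(1-w).
- Ratio, change to post: 2(1-w)/(1-b).
- Correlation of the post difference with the baseline difference: r = (w-b)/(1-b). Because the two differences have equal variance, r is also the efficient slope.
- Ratio, adjusted to post: (1-r²) × 14/13, the last factor being the approximate small-sample cost (n-2)/(n-3) at n = 16.

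Worked cases:

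- w = b: change ratio 2.00, SE factor √2 = 1.41; adjusted ratio 14/13 = 1.08.
- w = 0.8, b = 0.6: change ratio 2(0.2)/0.4 = 1.00; r = 0.2/0.4 = 0.5; adjusted ratio 0.75 × 14/13 = 0.81.

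Power is by simulation (40,000 trials per setting). The effect is 0.749 SDs of the post difference, which gives the paired post-injection t-test 80%. The adjusted analysis includes a sequence term. The serial settings let correlation decay over the actual visit days.

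| Setting | r | Variance, change/post | Variance, adjusted/post | Power, change | Power, adjusted |
|---|---|---|---|---|---|
| w = b = 0.5 | 0 | 2.00 | 1.08 | 51% | 76% |
| w 0.7, b 0.6 | 0.25 | 1.50 | 1.01 | 63% | 79% |
| w 0.8, b 0.6 | 0.50 | 1.00 | 0.81 | 80% | 87% |
| w 0.85, b 0.6 | 0.625 | 0.75 | 0.66 | 90% | 93% |
| Serial, 30-day 0.5 | 0.39 | 1.21 | 0.91 | 72% | 83% |
| Serial, 30-day 0.7 | 0.51 | 0.98 | 0.80 | 81% | 87% |
| Serial, 30-day 0.8 | 0.56 | 0.87 | 0.73 | 85% | 89% |
| Serial, 30-day 0.9 | 0.62 | 0.77 | 0.67 | 89% | 92% |

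**Where change would win.** Setting (1-r²) × 14/13 equal to 2(1-r) gives 1 + r = 26/14, so r is about 0.86. Raw change is better only above that.

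**Reference visit.** If both changes were taken from Visit 1, then (P1-B1) - (P2-B1) = P1 - P2. The baseline cancels and there is no inflation.

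**Carryover.** Suppose a fraction c of the effect remains at Visit 3 in sequence AB and none at Visit 4. With balanced sequences the change estimate is the effect × (1 + c/2), and the adjusted estimate is the effect × (1 + rc/2). For an assumed c = 0.30:

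- raw change overstates by 15%;
- adjusted overstates by 0% at r = 0, 7.5% at r = 0.5 (0.5 × 15%), and about 9% at the largest r in the table (0.625 × 15%);
- the post-injection contrast is unaffected.

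The simulation agrees with these.

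**The case against.** The strongest reply is that the cost may be small. Visits within a period are 30 days apart and the two post-injection visits are 90 days apart, so serial correlation is at least as plausible as equal correlation. From a 30-day correlation of about 0.7, change does as well as the post-injection contrast or better, and loses only some 3 to 6 power points to adjustment. This stands. A reader might infer that the planned test doubles the variance or is the worst simple choice. The documents do not support that: doubling requires w = b, and no correlation is given.

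The pairing is also inferred. The Visit 3 label and the Px1 pairing make it natural, but nothing states it for ARAT. This stands too, and is itself a reason to define the reference visit.

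A reader might extend the loss to Aim 1a. Its test sentence already uses post-injection values, so the loss arises there only if its opening sentence governs.

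A reader might also cite the eligibility text (Section III.ii), "within-individual intermittency and variability of rest tremor can be influenced by anxiety, stress, cold temperature, and fatigue", as proof of noisy ARAT baselines. That passage concerns tremor, and the same item provides up to 20 minutes of rest to limit the variability. A stress effect common to both injection days would cancel in the contrast.

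Finally, the pilot has no power target and reports non-significant tests as inconclusive. Power here serves only to rank the analyses; CI width depends on the same variances.

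**Conclusion.** The point holds as an avoidable and uncertain loss of precision in Aim 1b, on the natural reading of the change score. Across the settings examined, raw change has 51% to 90% power and the adjusted analysis 76% to 93%, with adjusted ahead each time. The formula is exact under equal variances; the power figures rest on assumed correlations, alpha and effect. Since the correlations are unknown, estimating the slope is safer than fixing it at 1.

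A reader might infer that the planned test is biased. Absent carryover it is not. Carryover at Visit 3 is possible under the plan's own expected duration, but the 30% is an assumption, and the adjusted analysis reduces the resulting bias without always removing it.

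**What to change.** In Section VI:

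1. State that the period baselines are Visit 1 and Visit 3.
2. For Aim 1b, and for Aim 1a so that its two sentences agree, regress each participant's toxin-minus-sham post-injection difference on the matching toxin-minus-sham baseline difference, plus a sequence term coded +1/-1.
3. Report the intercept, that is, the estimate at zero baseline difference, with its CI. Do not mean-centre the covariate: with balanced sequences that returns the unadjusted post-injection difference.
4. Report the unadjusted post-injection difference as a sensitivity analysis for carryover at Visit 3. It is not immune to effect lasting to Visit 4: a remaining fraction c' would shrink it by c'/2.

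The cost is a few sentences and two degrees of freedom, with no new data or visits. If the baselines carry no information, the loss against the post-injection t-test is about 4 power points (80% to 76%).
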